7.4.2 Administration

(i) Oral

One capsule at the prescribed dose is to be administered 45 minutes before the child's age-appropriate 'lights off' or 'snuggle-down-to-sleep' time.

This study is cogniscent of the current significant usage of melatonin on a named patient basis for children with neurodevelopmental disorders. It therefore recognises current clinical practice in those children who are unable or unwilling to swallow capsules. Current clinical practice involves opening the capsules and mixing them in a vehicle such as jam or yoghurt,

and for those patients with feeding tubes, suspending the contents of the capsules in water and administering the solution down the tube.

For participants unable or unwilling to swallow the capsules, the capsules may be opened and the content of the capsule mixed with the following vehicles:

- a. strawberry jam, 5ml
- b. strawberry yoghurt, 5ml
- c. orange juice, 10ml
- d. semi-skimmed milk, 10ml
- e. water, 10ml

When mixed in such a vehicle, it is recommended that it is administered to the participant immediately. If this is not possible, then it should be kept in the fridge and administered within 30 minutes of mixing. If not administered within 30 minutes the mixture should be thrown away.

[figure not shown]
The actual dose delivered will vary due to the method and accuracy of the opening and removal of the powder and the consumption of the food. It is clear from experimental work carried out that the accuracy of the dose is also determined by the dose and that lower dose capsules appear to retain relatively more melatonin drug substance in the shell than higher dose capsules. This method of dosing whilst not ideal is determined by the specific patient group being treated and should not prevent beneficial data being provided to the trial.

It will be noted on the eCRFs for those participants that require study medication to be administered in this manner the vehicle used to administer the study medication. Participants will be encouraged to mix the contents of the capsule with the same vehicle throughout the treatment period.

(ii) Via nasogastric/gastrostomy/jejunostomy tube

For children with nasogastric, gastrostomy or jejunostomy tubes the content of the capsule can be mixed with water, orange juice or semi skimmed milk and administered as normal.

Fig 2. Flow Diagram of Scheduled Treatment Dose Increase Steps

7.5 Unblinding

7.5.1 Unblinding of Individual Participants During Trial Conduct

Unblinding should be considered only when knowledge of the treatment assignment is deemed essential for the child's care by their physician or a regulatory body. In general, unblinding of participants during the conduct of the clinical trial is not allowed unless there are compelling medical or safety reasons to do so.

N.B. If simply ceasing study treatment is a viable option for the patient's care, it should not be necessary for unblinding to occur.

7.5.1.1 Procedure

- a. The decision to unblind a single case should be made when knowledge of an individual's allocated treatment is essential to:
 - i. enable treatment of serious adverse event/s, or
 - ii. enable administration of another therapy that is contraindicated by the trial treatment.
- b. Where possible, requests for individual unblinding should be made with the agreement of lead investigators [name] and/or [name] (contact should be made via the trial co-ordinator at the MCRN CTU, [name])
- c. In the event that it is considered necessary to unblind the participants allocation then the local investigator (or delegated other) should contact the pharmacy department of Alder Hey Hospital, Liverpool where the unblinding codes are held (see below for contact details)

Monday to Friday 0845 to 1730 hours Saturday/Sunday 0930 to 1600 hours	Telephone Pharmacy dispensary: [name] Ask for Senior Pharmacist, quoting MENDS unblinding service
All other times	Telephone Switchboard: [name] Ask that they contact the on-call pharmacist, quoting MENDS unblinding service

- d. Once contacted the Alder Hey Hospital Pharmacy will complete an unblinding CRF and release allocation of the individual patient only. The unblinding CRF will document:
 - i. Date information needed
 - ii. Detailed reason for unblinding
 - iii. Identity of recipient of the unblinding informationA copy of the unblinding CRF will be forwarded to the MCRN CTU within 24 hours of completion.
- e. The local investigator will ensure all necessary CRFs up to the time of unblinding are completed and submitted to MCRN CTU (if possible, completed *before* unblinding is performed). If the reason for unblinding is a serious adverse event all CRFs need to

be submitted to the MCRN CTU within 24 hours; otherwise CRFs can be submitted to MCRN CTU within 7 days.

- f. All instances of unblinding should be recorded and reported in writing to the MCRN CTU by the local investigator, including the identity of all recipients of the unblinding information.
- g. Allocation should not routinely be revealed to MCRN CTU personnel.

7.5.2 Accidental Unblinding

All instances of inadvertent unblinding should be recorded and reported in writing to the MCRN CTU by the local investigator. Reports to include:

1. Date of unblinding
2. Detailed explanation of circumstances
3. Recipients of the unblinding information
4. Action to prevent further occurrence
5. Allocation should not be routinely revealed to MCRN CTU personnel.

7.5.3 At Trial Closure

The end of the trial will be considered as the date of the final database lock, however the trial may be closed prematurely by the Trial Steering Committee, on the recommendation of the Data Monitoring Committee, for reasons such as clear differences between safety of trial treatments. Upon trial closure the Alder Hey Hospital pharmacy department will return unblinding codes to the MCRN CTU. MCRN CTU will notify local investigators in writing of unblinding information for patients under their care. A copy of this notification should be placed in the medical records and a copy retained in the site file. It is the responsibility of the local investigator to notify trial participants of their allocated treatment.

7.6 Accountability Procedures for Study Treatment/s

Throughout the study, patients will always be provided with a 7 day excess of their current treatment dose to allow for any unexpected delay in home or clinic visits. At randomisation (T0) the RP will collect 2 blister packs (7x0.5mg capsules in each) from pharmacy from the next patient pack to be assigned. The dispensing pharmacist will put the blister packs into a blank carton and put their local dispensing sticker (including patient name, patient address, pharmacy address and date) on to the carton, and will complete, sign and date the accountability log. The RP will also sign and date the accountability log. The RP will record the randomisation number on the pack in the eCRF. At each subsequent visit the RP will be provided with 1 blister pack (7 capsules) of the current dose, 2 blister packs of the next higher dose (if applicable) and 2 blister packs of the lower dose (if applicable, in case of dose reduction). The RP will ask the parents/guardians whether any doses have been missed during the preceding week and will check that this information corresponds with the number of capsules remaining in the blister pack. At each visit any extra medication and any used packages will be returned to the site pharmacy by the RP and will be signed for by the pharmacist who will record the number of capsules returned (See drug accountability log in Appendix I). At the end of the trial all medication will be returned to PENN for central destruction.

7.7 Assessment of Compliance with Study Treatment/s

Weeks T0 to T+4 (RP home visits)

The RP will collect all unused medication from the previous week at each home visit and a pill count will be conducted and recorded to determine that sufficient doses have been administered to enable dose increase, in accordance with section 7.9.1

All unused medication collected by the RP will be returned to pharmacy where they will be retained for the duration of the trial; at the end of the trial they will be returned to PENN for destruction.

Week T+11 (RP Home visit)

The RP will collect all unused medication from weeks T+5W to T+11W and a pill count will be conducted and recorded.

All unused medication collected by the RP will be returned to pharmacy where they will be retained for the duration of the trial; at the end of the trial they will be returned to PENN for destruction.

Week T+12 (clinic review)

The blister pack for week T+12W treatment regimen will be collected during the final trial assessment clinic visit and a pill count will be conducted and recorded. Any unused medication will be returned to pharmacy and retained for the duration of the trial; at the end of the trial returned to PENN for destruction.

Early withdrawal

If a patient wishes to withdraw from trial treatment, all unused medication will be collected and a pill count conducted and recorded. The unused medication will be returned to pharmacy and retained for the duration of the trial; at the end of the trial they will be returned to PENN for destruction.

7.8 Concomitant Medications/Treatments

7.8.1 Medications Permitted

Details of concomitant medication will be collected on the CRF at T0W and reviewed during weekly assessments (either during home visit/telephone call/clinic visit) between T0W and T+12W. The following concomitant medications, recorded at T0W, are permitted and must be documented on the eCRF:

- all anti-epileptics
- all stimulants
- all anti-depressants
- all mood changing drugs other than beta blockers
- all antibiotics

7.8.2 Medications Not Permitted/ Precautions Required

The following are not permitted for the duration of the trial period. If unavoidable for clinical reasons then the patient will be withdrawn from the trial:

- melatonin (other than the study treatment)
- all beta-blockers
- consumption of alcohol
- sedative / hypnotic drugs (including chloral hydrate, alimemazine tartrate (Vallergan) and Triclofos)

The following drugs in particular should not be commenced (although if patients have been treated with them at a stable dose for 2 months prior to the date of screening they can be entered into the study), if possible, during the trial period. However if necessary their use is permitted and should be documented on the eCRF:

- any benzodiazepines
- amisulpride (Solian)
- chlorpromazine (Largactil)

- haloperidol (Haldol)
- olanzapine (Zyprexa)
- risperidone (Risperdal)
- sertindole (Serdolect)
- sulpiride (Sulpidil, Sulpor)
- thioridazine (Melleril)
- trifluoperazine (Stelazine)

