5.3.2 Withdrawal from Trial Intervention

Patients may be withdrawn from treatment for any of the following reasons:

- a. Parent/ legal representative (or, where applicable, the patient) withdraws consent for treatment.
- b. Unacceptable adverse effects.
- c. Intercurrent illness preventing further treatment.
- d. Development of serious disease preventing further treatment.
- e. Any change in the patient's condition that justifies the discontinuation of treatment in the clinician's opinion.

If a patient wishes to withdraw from trial treatment, centres should document the reason and explain the importance of remaining on trial follow-up and, if willing, to still have data collected as per trial schedule (actigraphy, sleep and seizure dairies, questionnaires etc), or failing this, to attend clinic and allow routine follow-up data to be used for trial purposes. Generally, follow-up will continue unless the patient explicitly also withdraws consent for follow-up (see section 5.3.3). Following withdrawal from trial treatment patients will be treated according to usual local clinical practice.

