5.3.3 Withdrawal from Trial Completely

Patients are free to withdraw consent at any time without providing a reason. Patients who wish to withdraw consent for the trial will have anonymised data collected up to the point of that withdrawal of consent included in the analyses. The patient will not contribute further data to the study and the MCRN should be informed in writing by the responsible physician and a withdrawal CRF should be completed. Data up to the time of withdrawal will be included in the analyses unless the patient explicitly states that this is not their wish.

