9.6 Analysis Plan

The study will be analysed and reported following the 'CONSORT' guidelines (Consolidated Standard of Reporting Trials)⁽³⁸⁻⁴¹⁾.

Data from all the study children will be analysed on completion of the study (T12W) on an intention to treat basis.

All analyses will be pre-specified in detail in the statistical analysis plan and agreed by both the Trial Steering Committee and the Data Monitoring Committee prior to the internal pilot.

Missing data will be handled by considering the robustness of the complete case analysis to sensitivity analyses using various imputation assumptions; however these will be informed by data collected on the reasons for missing data.

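### Section 7.8.2 withdraws a child who needs a listed medicine from the trial; read literally, this ends outcome collection and conflicts with sections 5.3.2 and 9.6

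*Protocol*

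**What the plan says.** Protocol section 7.8.2 lists four items that are not permitted during the trial period: melatonin other than study treatment, beta-blockers, alcohol, and sedative or hypnotic drugs. Its rule is: "If unavoidable for clinical reasons then the patient will be withdrawn from the trial". A second list in the same section (benzodiazepines and named antipsychotics) is treated differently: "However if necessary their use is permitted and should be documented on the eCRF".

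The protocol describes two kinds of exit.

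- Section 5.3.2, on withdrawal from the intervention: "Generally, follow-up will continue unless the patient explicitly also withdraws consent for follow-up". It names actigraphy, diaries and questionnaires as data still to be collected, and adds: "Following withdrawal from trial treatment patients will be treated according to usual local clinical practice".
- Section 5.3.3, on complete withdrawal: "The patient will not contribute further data to the study". Earlier data are kept: "Data up to the time of withdrawal will be included in the analyses unless the patient explicitly states that this is not their wish".

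On analysis, section 9.6 says: "Data from all the study children will be analysed on completion of the study (T12W) on an intention to treat basis". The same section takes a complete-case analysis as the base and tests it against imputation assumptions. Section 9.3.1 defines the primary comparison as week T-1W against week T+11W, with at least 5 of 7 diary nights required.

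**The concern.** Section 7.8.2 is mandatory and does not depend on any withdrawal of consent. Its wording is that of complete withdrawal, and it does not say whether diaries continue. A site could reasonably stop collecting outcomes when a listed medicine is started. Another site, reading 5.3.2, could reasonably carry on.

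This affects the primary result in two ways. First, the primary outcome sits in one late week, so a child whose diary stops earlier contributes nothing to the complete-case comparison. Secondly, two of the four listed items are treatments for poor sleep. Children who start them may well be those whose sleep has not improved, so the missing data may be related to the outcome. If such exits are more frequent on placebo, the remaining placebo group looks better than it was and the estimated effect shrinks. If they are more frequent on melatonin, the effect is exaggerated.

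**Working it through.** **Passages side by side**

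| Place | Trigger | Data afterwards |
|---|---|---|
| 5.3.2 | Stopping trial treatment, including for clinical reasons | Continue by default |
| 5.3.3 | Withdrawal of consent for the trial | None |
| 7.8.2 | Unavoidable need for a listed item | Not stated; wording is that of leaving the trial |
| Table 2, Premature Discontinuation column | Early stop | Concomitant medication and adverse events; examination and vital signs as indicated; no diary, actigraphy or questionnaire |
| 9.6 | All study children | Analysed by intention to treat |

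One case shows the clash. A child stops study drug and is then given melatonin under usual local care. Section 5.3.2 keeps that child in follow-up; section 7.8.2, read literally, removes the child.

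**The plan's own figure**

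Inputs from section 9.4: difference 1 h, SD 1.7 h, two-sided 0.05, power 80%, t-test. The normal approximation 2 × (1.960 + 0.842)² × (1.7/1)² gives 45.4, so 46 per group. The noncentral t calculation gives 46.35, so 47, as stated. The stated 57 is 47 × 1.2 = 56.4, rounded up.

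**Bias if data do end**

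Assume normal change scores with SD 1.7 h in each arm. A share q of an arm is removed, and r is the correlation between being removed and having a poor change score. The mean of those remaining rises by r × 1.7 × φ(z_q)/(1 − q), where z_q is the normal quantile and φ the normal density. The shares and r are assumptions; the protocol gives neither.

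- q = 5%: 1.7 × 0.1031/0.95 = 0.185 h at r = 1
- q = 10%: 1.7 × 0.1755/0.90 = 0.331 h at r = 1
- q = 20%: 1.7 × 0.2800/0.80 = 0.595 h at r = 1

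The apparent difference for a true 1.00 h is 1 − (placebo shift) + (melatonin shift):

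| Placebo v melatonin removed | r = 1 | r = 0.5 | r = 0.3 |
|---|---|---|---|
| 10% v 10% | 1.00 | 1.00 | 1.00 |
| 10% v 5% | 0.85 | 0.93 | 0.96 |
| 20% v 10% | 0.74 | 0.87 | 0.92 |
| 10% v 0% | 0.67 | 0.83 | 0.90 |
| 5% v 10% | 1.15 | 1.07 | 1.04 |

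The r = 1 column is a worst case: those removed are exactly the poorest responders.

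**Power**

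With 57 per group and the planned 20% loss, 57 × 0.80 = 45.6 remain and power for 1 h is 79.3%. If these exits came on top of that allowance, adding 5, 10 or 15 percentage points, power would be 76.7%, 73.7% or 70.5%. If the 20% already covers them, there is no further loss.

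**The case against.** A reader might infer that 7.8.2 definitely ends these children's data, removes treatment failures selectively and so breaks the intention-to-treat analysis. The documents do not go that far.

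- Section 7.8.2 cites neither 5.3.2 nor 5.3.3. Section 5.3.3 is written for withdrawn consent, which a clinically needed medicine does not involve. Section 5.3.2 covers clinical reasons and makes continued follow-up the default, and section 5.3 asks for continued evaluations even after voluntary withdrawal.
- Section 11.4 speaks of leaving trial treatment and leaving the trial in adjacent sentences, apparently about the same children. The protocol therefore does not use the second phrase strictly.
- Table 2's column does not cancel scheduled visits.
- Use of beta-blockers or alcohol is not treatment failure, and benzodiazepines and the named antipsychotics may be started without withdrawal.
- Data before withdrawal are kept. Section 9.5 provides for collecting reasons for missing data, and section 9.6 plans imputation sensitivity analyses informed by them.

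All of this stands against the stronger reading, and it means that bias is possible rather than shown. It does not remove the point. The literal wording still favours complete withdrawal, sites can act differently on it, and neither earlier diaries nor imputation replaces a T+11W diary that was never collected.

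**Conclusion.** The point holds as an unresolved conflict of wording with a plausible effect on the primary comparison. Taken literally, 7.8.2 costs a child the T+11W outcome without any withdrawal of consent, against the default in 5.3.2 and the principle in 9.6. That data end is the literal reading, not an express statement.

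The size and direction of any bias depend on arm-specific rates that the protocol does not give. At an assumed 10% v 5%, the loss from a true 1.00 h is about 0.15 h at worst and 0.04 to 0.07 h under weaker selection. It is nil if removal and selection are equal in both arms, and the sign reverses if more melatonin children leave. The case for acting rests on the cheapness of the correction and on the fact that uncollected primary-week diaries cannot be recovered.

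**What to change.** Reconcile 7.8.2, 5.3.2, 5.3.3 and Table 2 so that they state together that:

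- use of a listed medicine does not by itself end data collection;
- the medicine and its start date are recorded;
- diaries, actigraphy and questionnaires continue to T+12W unless consent for follow-up is withdrawn, and Table 2 shows this;
- these data enter the intention-to-treat analysis.

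A bare cross-reference from 7.8.2 to 5.3.2 would not be enough. That section concerns withdrawal from the intervention, so the reference would imply that study drug stops. The amendment should be confined to data collection. Which medicines are allowed, and whether study drug continues, are left to the sponsor.

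The cost is a wording amendment, since the remaining visits and calls are already scheduled. The downside is that some outcomes will be measured on other sleep medication, which a sensitivity analysis can address.

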7.8.3 Data on Concomitant Medication

Dose and names of all concomitant medication should be documented on the eCRF at T0W. This will be reassessed weekly by the RP throughout trial participation; during home visits, telephone contact or clinic review. Any new medications introduced or changes to medications during the trial period should be documented on the eCRF.

7.9 Dose Modifications

7.9.1 Stepped dose increases (Weeks T+1 to T+4 (also T+5 and T+6)

At each home visit the RP will review the sleep and seizure diary and Treatment Emergent Signs and Symptoms (TESS; section 8.4.2) in order to make an overall assessment of treatment effect. If a dose increase is to be undertaken the following criteria should all be met:

- (i) absence of Serious Adverse Events
- (ii) a minimum of 5 of 7 days completed in the sleep diary
- (iii) no 'significant increase'* in seizure activity (where applicable)
- (iv) child having received at least 5 of the possible 7 doses in the current week and
- (v) a) child not falling asleep within one hour of 'lights off' or 'snuggling down to sleep' at age-appropriate times for the child in three nights out of five **, and/or
b) child having less than 6 hours of continuous sleep in three nights out of five.

* Defined as a doubling in seizure activity over the preceding four weeks

** This will be the child's usual bedtime based upon the family's normal routine

If any of the criteria are not met, or if there is any doubt, the current dose should be maintained.

7.9.2 Dose reductions, interruptions or permanent discontinuation

The decision to reduce, interrupt, or discontinue trial therapy is at the discretion of the treating clinician. Doses may be reduced, interrupted or discontinued at any time during the trial period for reasons such as unacceptable adverse effects (e.g. unacceptable increase in daytime fatigue, unacceptable behavioural change, doubling in the number of seizures during the preceding four weeks, unacceptable increase in number or severity of headaches), intercurrent illness, development of serious disease or any change in the patient's condition that justifies the modification of treatment in the clinician's opinion.

Prior to modifications of trial therapy the RP will consult (via telephone) with the local PI (or appropriate clinician listed on the site delegation log) or one of the lead investigators ([name] or [name]). If a dose reduction is agreed upon and the decision is made during the home visit then the family will be provided with the preceding dose.

In the event that neither a local investigator nor one of the lead investigators are available until the next working day, that evenings dose of melatonin will be omitted, until the decision to modify the dose has been confirmed by an appropriate clinician. At this point if a decision to reduce the dose is confirmed then an additional unscheduled home visit will be arranged as soon as possible in order for the RP to provide sufficient melatonin of the previous strength for the time period until the next scheduled home or clinic visit. Any doses of

melatonin scheduled between the time of the decision to lower the dose and the day of the unscheduled visit would be omitted. An unscheduled visit would also be arranged if a dose reduction is thought to be required following a scheduled telephone call. Modifications of trial therapy should be documented on the eCRF.

